4.2 Treatment Groups

Treatment groups in the DBT phase are rimegepant 75 mg and placebo. The treatment group in the OLE phase is rimegepant 75 mg.

Populations of treated subjects will be assessed by the as-treated treatment group; i.e., by the treatment actually received. Otherwise, all other populations and all efficacy analyses will be assessed by the as-randomized treatment group. The enrolled population will be assessed overall.

5 SAMPLE, POWER, AND TYPE I ERROR

The sample size for this study will be approximately 60 randomized patients. Approximately 120 patients will be screened, assuming no more than 50 percent of patients would be ineligible for randomization.

The calculation for the sample size was based on a paired t-test crossover design, assuming a low correlation ($r = 0.2$) between the active and placebo response to treatment. Assuming a paired difference standard deviation of 3.8, 60 randomized patients will provide $>90\%$ power to detect a 2-point difference between rimegepant and placebo using a two-sided significance level of 0.05 and a 20% dropout rate with no imputation.

Type 1 error is not applicable. The significance of the primary and secondary endpoints will not be evaluated.

6 STATISTICAL ANALYSES

6.1 General

6.1.1 *Programmed Output*

A list of TLFs and corresponding templates are presented separately in a mock TLF document corresponding to this SAP.

Refer to the Core SAP for additional details about programmed output.

Medical history and AEs are coded using the Medical Dictionary for Regulatory Activities (MedDRA) most recent version available.

Concomitant medications are coded using the World Health Organization Drug Global Dictionary (WHODrug Global), most recent version available.

All statistical analyses will be performed using SAS statistical software (Version 9.4 or higher), unless otherwise noted.

6.1.1.1 *Tables*

Tables will be summarized by treatment sequence and period, rimegepant pooled, placebo pooled, and overall. Exceptions are specified in subsequent sections as needed.

6.1.1.2 *By-Subject Listings*

By-subject listings will present all data by randomization status (randomized, not randomized), site-subject ID, and additional variables such as time points, as applicable. Listings display as-randomized treatment sequence abbreviated as (1) “RMG-PBO” for Sequence 1 subjects, “PBO-RMG” for Sequence 2 subjects, and (2) “NRND” for subjects who are not randomized.

Refer to the Core SAP for additional details about listings.

6.1.2 *Statistical Methods*

Refer to the Core SAP for descriptive statistics in summary tables, counting rules in frequency tables, and rounding rules.

Categorical variables will be tabulated with the count and percentage within each category (with a ‘Missing’ category if applicable). Continuous variables will be summarized with univariate statistics (e.g., n, mean, median, standard deviation (SD), minimum, and maximum).

Tabulations of the following endpoints present the number of unique subjects with an event: protocol deviations; non-study medications; AEs; and laboratory abnormalities. Thus, for these endpoints, multiple occurrences of the same event are counted only once per subject.

6.1.3 *Handling of Missing Data*

Unless otherwise noted, efficacy analyses will be based on observed data only. For the main analyses of efficacy for primary and secondary endpoints, no imputation will be performed to impute data following discontinuation from study.

For efficacy analyses, partial or missing dates will not be imputed. The relative study days, where determined, will be calculated for full dates only.

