Study Design:	
BHV3000-202 is a phase 2, multi- center, double-blind, placebo controlled, crossover trial to assess the safety, tolerability, and efficacy of rimegepant in treating Trigeminal Neuralgia in patients who failed to respond adequately to or had intolerance or a contraindication to pharmacotherapy. Current inadequate response to therapy is defined by a daily pain score of greater than or equal to 4 on the “average intensity”, on the 11 point Numerical Pain Rating Scale during the 14 days prior to baseline. A crossover design with a placebo washout period of 7 days between treatments will be used due to the limited number of subjects, with each patient serving as their own control. The study will be conducted at multiple centers.
 
Prior to randomization, patients will enter a 14-30 day screening period during which they will complete daily self-reported assessments of pain intensity over a 24 hour period using an 11 point Numeric Pain Rating Scale, ranging from 0 (for no pain) to 10 (for the worst imaginable pain.) Throughout the study, patients will be allowed to remain on their current medication regimens, provided they are on a stable dose for a minimum of 4 weeks prior to randomization visit.
 
Patients with a mean of <math>\geq 4</math> on the daily “average intensity” on the 11 point Numeric Pain Rating Scale, during the 14-30 day screening period, will be randomized to one of two treatment sequences to receive rimegepant 75 mg immediate release (IR) tablet administered orally vs placebo. Each sequence will include a 2 week treatment phase, with daily dosing of study drug/medication or placebo. This will be followed by a 7 day placebo washout period. After the placebo washout period, another 2 week treatment phase will follow, again with once daily dosing of study drug/medication or placebo. In the first sequence, patients will receive placebo for the first treatment period and rimegepant 75 mg IR tablet during the second treatment period. The second sequence will have rimegepant 75 mg IR tablet during the first 2 week treatment period, followed by placebo in the second treatment phase. For subjects, this design should seem like a “seamless” 5 week treatment phase.
 
During each 2 week treatment phase and during the 7 day placebo washout period, patients will complete the 11 point Numeric Pain Rating Scale daily, as described above. In addition, patients will complete a paper diary daily to record efficacy data. The diary will include the daily recording of overall pain using the 11 point numeric pain rating scale, a recording of daily use of rescue medications, and a daily rating of worst pain episode using the 11 point Numeric Pain Rating Scale. This data will be entered into the CRF. Other secondary

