### **3.5.2      Randomization Phase (35 Days)**

Patients with a mean score of greater than or equal to 4 on the daily “average intensity” 11 point Numeric Pain Rating Scale, during the 14 to 30 day screening period, will be randomized to one of two treatment sequences to receive BHV-3000 (75 mg QD) administered orally vs placebo (QD) in a 1:1 ratio. Patients should be encouraged to take their dose of medication in the mornings. Patients with a diagnosis of typical and atypical TN will be stratified equally into the two sequences; and patients with atypical TN will not exceed 50% of the subjects. Each sequence will include a 2 week treatment phase, with daily dosing of study drug/medication or placebo. This will be followed by a 7 day placebo washout period. After the placebo washout period, another 2 week treatment phase will follow, again with once daily dosing of study drug/medication or placebo. In the first sequence, patients will receive placebo for the first treatment period and BHV-3000 75 mg during the second treatment period. The second sequence will have BHV-3000 75 mg during the first 2 week treatment period, followed by placebo in the second treatment phase.

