### **6.2.2 Selection and Timing of Dose Administration**

During the Double-Blind Phase of the study, subjects will be randomized to a sequence of either rimegepant (75 mg QD) and then placebo or placebo then rimegepant (75 mg QD) in a 2-sequence, 2-period, crossover design. Study drug/medication will be dispensed at the baseline visit and at Days 14 and 21. Subjects should take the first dose the day of the baseline visit. Study drug/medication should be administered in the morning without regard to meals. Subjects who showed continued compliance during the Double-Blind Phase may choose to enter a 12 week Open-label Extension Phase with daily dosing of rimegepant (75 mg QD) ODT. Open-label study drug/medication will be dispensed at Day 35 visit for subjects who enter the Open-label Extension Phase. Subjects should take the first dose of OLE study drug/medication on Day 36.

During the Open-label Extension Phase, if a dose of study drug/medication for a given day is missed, lost, or otherwise unable to be taken, the subject should document that as a missed dose on the **subject paper study log**.

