2 STUDY DESCRIPTION

2.1 Study Design

BHV3000-202 is a phase 2, multi-center, double-blind, placebo controlled, crossover trial to assess the safety, tolerability, and efficacy of rimegepant in treating TN in patients who failed to respond adequately to or had intolerance or a contraindication to pharmacotherapy. Current inadequate response to therapy is defined by a daily pain score of greater than or equal to 4 on the “average intensity” on 11-point Numerical Pain Rating Scale (NPRS) during the 14 days prior to baseline. A crossover design with a placebo washout period of 7 days between treatments will be used due to the limited number of subjects, with each patient serving as their own control. The study will be conducted at multiple centers.

Figure 1 displays the study design.

Figure 1: Study Schematic

Prior to randomization, patients will enter a 14 to 30 day screening period during which they will complete daily self-reported assessments of pain intensity over a 24 hour period using an 11 point NPRS, ranging from 0 (for no pain) to 10 (for the worst imaginable pain). Throughout the

study, patients will be allowed to remain on their current medication regimens, provided they have been on a stable dose for a minimum of 4 weeks prior to the randomization visit.

Patients with a mean of ≥ 4 on the daily “average intensity” on the 11 point NPRS, during the last 14 days of the screening period, will be randomized to one of two treatment sequences to receive rimegepant 75 mg immediate release (IR) tablet administered orally vs placebo. Each sequence will include a 2-week treatment phase, with daily dosing of study drug or placebo. This will be followed by a 7-day placebo washout period. After the placebo washout period, another 2-week treatment phase will follow, again with once daily dosing of study drug or placebo. In the first sequence, patients will receive placebo for the first treatment period and rimegepant 75 mg IR tablet during the second treatment period. The second sequence will receive rimegepant 75 mg IR tablet during the first 2 week treatment period, followed by placebo in the second treatment phase.

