During the DBT Phase of the study, subjects will be randomized to a sequence of either rimegepant (75 mg QD) and then placebo or placebo then rimegepant (75 mg QD) in a 2-sequence, 2-period, crossover design. Study drug/medication will be dispensed at the baseline visit and at Days 14 and 21. Subjects should take the first dose the day of the baseline visit. Study drug/medication should be administered in the morning without regard to meals. Subjects who showed continued compliance during the DBT Phase may choose to enter a 12 week OLE Phase with daily dosing of rimegepant (75 mg QD) ODT. Open label study drug will be dispensed at the Day 35 visit for subjects who enter the OLE Phase. Subjects should take the first dose of OLE study drug on Day 36.

Subjects report study drug exposure in the subject paper study log (diary), whereas sites report study drug accountability on the Study Drug Dispensing Log CRF.

An administrative listing of IP batch numbers is provided for the treated analysis set. Refer to the Core SAP for listing contents.

DB Study Drug (Rimegepant or Placebo) Exposure

DB rimegepant or placebo exposure will be summarized descriptively by as-treated treatment groups for period 1 placebo, period 1 rimegepant, period 2 rimegepant, period 2 placebo, rimegepant pooled, placebo pooled and overall, and will include the following parameters:

- Time on DBT (days), derived as DBT end date – DBT start date + 1
- Time on DBT study drug category (weeks)
- Cumulative DBT exposure (mg), derived by summing number of DB mg across DB study drug records
- Average DBT exposure (mg per day), derived as cumulative DB exposure/time on DBT
- Total DBT exposure (tablets) summed across all subjects, derived by summing cumulative DB exposure across all subjects.
- Total DBT exposure (patient-years), derived by summing (DBT end date – DBT start date + 1)/365.25 across all subjects.

OL Rimegepant Exposure

OL rimegepant exposure will be summarized descriptively by treatment sequence and overall, and will include the following parameters:

- Time on OL rimegepant (days), derived as OL rimegepant end date – OL rimegepant start date + 1
- Time on OL rimegepant category (weeks)
- Cumulative OL rimegepant exposure (mg), derived by summing number of OL mg across records with non-missing OL rimegepant date/times.
- Average OL rimegepant exposure (mg per day), derived as cumulative OL rimegepant exposure/time on OL rimegepant

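### Do the SAP's Sequence 1 and Sequence 2 labels contradict the design text in a way that requires a change to the plan?

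*SAP*

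**What the plan says.** The only place that uses numbered sequence codes is the listing convention in SAP 6.1.1.2: "RMG-PBO” for Sequence 1 subjects, “PBO-RMG” for Sequence 2 subjects". Subjects who were not randomised get a third abbreviation. The rule governs display of the as-randomised sequence in by-subject listings.

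Three places describe the two arms in prose, in the opposite order:

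- SAP 2.1: "In the first sequence, patients will receive placebo for the first treatment period and rimegepant 75 mg IR tablet during the second treatment period", and then "The second sequence will receive rimegepant 75 mg IR tablet during the first 2 week treatment period".
- Protocol Study Summary: the same first sentence as SAP 2.1, followed by "The second sequence will have rimegepant 75 mg IR tablet during the first 2 week treatment period".
- Protocol 3.5.2: "In the first sequence, patients will receive placebo for the first treatment period and BHV-3000 75 mg during the second treatment period", and "The second sequence will have BHV-3000 75 mg during the first 2 week treatment period, followed by placebo in the second treatment phase".

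Two further places name both orders without numbering them, with rimegepant-first mentioned first. Protocol 6.2.2 speaks of "a sequence of either rimegepant (75 mg QD) and then placebo or placebo then rimegepant (75 mg QD"), and SAP 6.2.6.1 repeats the wording.

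No text supplied reconciles the numbering. The schematics are not reproduced in the text, and the Core SAP, mock TLF document and IWRS specification are not among the documents reviewed.

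**The concern.** A programmer or reader who takes the first sequence in SAP 2.1 to mean Sequence 1 gets placebo-then-rimegepant. The same person applying SAP 6.1.1.2 prints RMG-PBO for Sequence 1. The SAP then appears to contradict both itself and the protocol on which it is based.

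In a two-period crossover the sequence label is how a listing reader works out which treatment a subject was assigned in period 1 and in period 2. The efficacy listing in SAP 6.3 is organised by treatment sequence and period, and the adverse-event listing in SAP 6.4.1 carries the same label. If the label were reversed, someone reading an individual subject's pain scores or adverse events would attribute them to the wrong treatment.

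SAP 2.3 adds to the worry. Draft outputs before the double-blind database lock use dummy treatment groups, so a blinded dry run would not be expected to expose a reversed label.

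**Working it through.** No figure in the plan depends on this point, so there is none to reproduce. The check has four steps.

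**1. Set the statements side by side.**

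| Place | Placebo then rimegepant | Rimegepant then placebo |
|---|---|---|
| SAP 6.1.1.2 | Sequence 2 (code) | Sequence 1 (code) |
| SAP 2.1 | first (prose) | second (prose) |
| Protocol Study Summary | first (prose) | second (prose) |
| Protocol 3.5.2 | first (prose) | second (prose) |
| Protocol 6.2.2 | named second, no number | named first, no number |
| SAP 6.2.6.1 | named second, no number | named first, no number |

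Three prose statements run one way and one coded statement runs the other. Two unnumbered statements use the coded order. The order of mention is therefore not fixed across the documents, and first and second in prose may be no more than order of description.

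**2. What must be true for a listing to be wrong.** Two conditions are needed together:

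- (a) the IWRS numbers placebo-then-rimegepant as 1;
- (b) the listing label is decoded from that number by the SAP 6.1.1.2 rule, rather than taken from the treatments assigned by period.

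If (a) is false, the rule decodes correctly. If (b) is false, the label is correct whatever the numbering. With both true, the displayed order is reversed for every randomised subject. At the planned size and 1:1 allocation that is 60 / 2 = 30 per sequence, or 60 in all, in listings that cover all randomised subjects. The laboratory listing (grade 3 or 4 abnormality, or a positive pregnancy test), the liver-test listing (values above set thresholds) and the deaths listing cover only subsets. The actual number randomised before the early termination is not given.

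**3. Effect on the estimates.** The SAP 6.3.1 model can be written

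y = μ + τT + γS + πP + βB + u + e,

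with T treatment (0/1), S sequence (1/2), P period, B baseline, u the subject effect and e the error.

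- Renumber the sequences: S* = 3 − S. Then γS = 3γ − γS*. The intercept moves by 3γ and the sequence coefficient changes sign. The treatment effect τ is untouched.
- Swap the treatment variable itself: T* = 1 − T. Then τT = τ − τT*. The treatment estimate changes sign and keeps its standard error. In a simulated crossover (48 subjects, assumed data) the estimate went from −1.388 to +1.388, with SE 0.211 both times.

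The second case is a different error. It requires the analysis treatment variable to be built from a wrongly decoded sequence number. The SAP 6.1.1.2 rule concerns what listings display, and nothing in the documents says that treatment is derived through it.

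**4. What would expose a reversal.**

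- SAP 6.2.1 already plans an administrative listing of the randomisation scheme and codes for every randomisation number, against which the label can be read directly.
- Protocol 6.2.1 has the IWRS assign specific bottle numbers, so the treatment dispensed can be traced without a sequence number.
- The exposure, compliance and non-study medication tables (SAP 6.2.6.1 to 6.2.6.3) have columns named by period and treatment.
- SAP 6.2.6.2 counts subjects who took incorrect study drug. If treatment received is derived from dispensing records, a reversed assigned order would put nearly every subject in that category.

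**The case for a change.** The strongest case for acting has three parts.

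First, the three prose passages agree with each other and use first and second as names for the arms, so reading them as Sequences 1 and 2 is natural. That stands: the wording should match, and no text supplied makes it match.

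Second, a definition in the Core SAP would not remove the discordant line, because SAP 1 gives the Core SAP primacy only where this SAP is silent or refers to it directly. That is right about precedence. It still leaves open that the schematic, mock TLF document or IWRS specification already tells programmers the numbering.

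Third, SAP 4.2 analyses efficacy by as-randomised treatment. If that assignment were decoded the wrong way round, the rimegepant-placebo difference would change sign, which is far worse than a mislabelled listing. The arithmetic is correct, but the premise is not in the documents. It would be a programming failure affecting every subject at once. It would disagree with the randomisation-code listing and, where treatment received is derived independently, with the exposure tables. Verification of programs against the randomisation list deals with that risk; the order of two sentences in SAP 2.1 does not.

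The point about dummy treatment groups also holds for blinded drafts. Outputs after the double-blind lock are produced unblinded under SAP 2.3, and the labels can be compared with the randomisation codes at that stage.

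**Conclusion.** The inconsistency is real as wording: SAP 6.1.1.2 numbers the sequences in the opposite order to the prose in SAP 2.1, the protocol Study Summary and protocol 3.5.2. It is a clerical slip with no demonstrated consequence. The printed abbreviations state the treatment order, so a reader of the listings never needs the number. Harm requires both the IWRS numbering and the decode to go the wrong way. If both did, up to 60 planned subjects would be displayed in reverse order; otherwise none would.

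Renumbering the sequences has no effect on the treatment estimate, and SAP 5 states that significance will not be evaluated. This rests on one assumption: that the treatment variable is not itself built from a wrongly decoded sequence number. The documents give no reason to think it is.

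Confidence is high that the wording differs. The documents cannot show which numbering the IWRS uses. An analyst working from the randomisation list would resolve the point without instruction, and the listing needed to confirm it is already planned. The wording can be tidied if the SAP is reopened for another reason, but no change to the plan is required.

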6.2 Study Population

6.2.1 Analysis Sets

The number of subjects in each analysis set described in Section 4.1 is tabulated by treatment sequence (as-randomized for the full and mITT analysis sets; as-treated for the treated analysis set), not randomized, and overall.

A by-subject listing of analysis sets is provided for the enrolled analysis set, which includes the reason for exclusion (i.e., not treated with study drug). Treated subjects may have > 1 exclusion reason.

A by-subject administrative listing of randomization scheme and codes is provided for all randomization numbers and block numbers, even those not assigned to a subject.

6.2.2 Enrollment

Enrollment by country and site is tabulated overall for the enrolled analysis set, full analysis set, and safety analysis set.

6.2.3 Subject Disposition

Results are based on the Study Termination Summary case report form (CRF). A by-subject listing of subject disposition by study phase will be produced for the enrolled analysis set. Refer to Section 6.2.3.1 of the Core SAP for more details.

6.2.3.1 Subject Disposition during the DBT Phase

Subject disposition during the DBT phase will be summarized for treated subjects by as-treated treatment sequence and overall as the number and percentage of subjects in the following categories:

- Completed the first treatment period
- Withdrawn from the first treatment period
 - Reasons for withdrawal, including not reported
- Completed the second treatment period
- Withdrawn from the second treatment period
 - Reasons for withdrawal, including not reported.
- Continuing to the OLE phase
- Not continuing to the OLE phase

6.2.3.2 Subject Disposition during the OLE Phase

Subject disposition in the OLE phase will be summarized for OLE treated subjects overall as the number and percentage of subjects in the following categories:

- Completed the OLE Phase
- Withdrawn from the OLE Phase
 - Reasons for withdrawal, including not reported.

6.2.3.3 *Subject Disposition during the Follow-Up Phase*

Subject disposition in the follow-up phase will be summarized for treated subjects overall as the number and percentage of subjects in the following categories:

- Completed the follow-up safety visit
- Did not complete the follow-up safety visit
 - Reasons for not completing

6.2.4 *Protocol Deviations*

6.2.4.1 *Relevant Protocol Deviations*

The frequency table of relevant protocol deviations are provided as the number and percentage of subjects in deviation categories by treatment sequence and overall for the full analysis set. Results are shown by deviation type (eligibility, subject management), category, and subcategory in the order specified in Section 9.1. Results for all relevant protocol deviation categories and subcategories are displayed, even those with 0 counts, unless specified otherwise. See Section 6.2.4.1 of the Core SAP for further details.

A by-subject listing of relevant protocol deviations is provided for the full analysis set. This includes deviation type, category, and subcategory, which are additional sorting variables.

6.2.4.2 *Significant Protocol Deviations*

Significant protocol deviations are non-programmable deviations that do not impact the interpretability of study data. A subject listing of significant protocol deviations is a manually generated appendix provided by clinical operations for inclusion in the CSR.

A by-subject listing of significant protocol deviations is provided for the enrolled analysis set. This includes visit, deviation type, deviation description, and specify, which are used as additional sorting variables.

6.2.5 *Baseline Characteristics*

Baseline characteristics include: (1) demographics and other relevant baseline characteristics, (2) neurological exam results, (3) medical history, and (4) non-study prior medications. Tables will be summarized by treatment sequence and overall, unless otherwise specified.

Tables of baseline characteristics are provided for the DBT treated analysis set.

The frequency table of randomization stratum (i.e., atypical and typical TN) is provided for the full analysis set by as-randomized treatment sequence and overall.

For the DB treated and Follow-up treated analysis set, baseline is defined as the last non-missing value at or before the study drug start date/time (rimegepant or placebo) during period 1 of the 2-period sequence. For other analysis sets, refer to the Core SAP for details on baseline for a parameter (e.g., weight), including handling of ties on the same measurement date. For the OL

rimegepant treated analysis set, baseline is defined as the last non-missing value at or before the OL study drug start date/time.

By-subject listings are provided for the enrolled analysis set for (1) through (4) above.

6.2.5.1 *Demographics and Other Relevant Baseline Characteristics*

Refer to the Core SAP for the table of demographics and other relevant baseline characteristics, and calculating age at a reference date. Other relevant characteristics also include the following: neuralgia type (typical, atypical), MRI confirmed Classical TN diagnosis (yes, no).

6.2.5.2 *Medical History*

The frequency table of medical history is provided by system organ class (SOC) and preferred term (PT), and displayed in descending order of overall frequency within SOC and PT. Refer to the Core SAP (Section 6.2.5.3) for medical history.

6.2.5.3 *Non-study Prior Medications*

Frequency tables of non-study prior medications (i.e., previous or current medications) is provided by therapeutic class and preferred name in descending order of overall frequency within therapeutic class and preferred name. The definitions of medication types in Section 6.2.6.3 of the Core SAP applies.

6.2.6 *Exposure*

Analyses are based on as-treated treatment group to support safety, unless specified otherwise.

6.2.6.1 *Study Therapy*

During the DBT Phase of the study, subjects will be randomized to a sequence of either rimegepant (75 mg QD) and then placebo or placebo then rimegepant (75 mg QD) in a 2-sequence, 2-period, crossover design. Study drug/medication will be dispensed at the baseline visit and at Days 14 and 21. Subjects should take the first dose the day of the baseline visit. Study drug/medication should be administered in the morning without regard to meals. Subjects who showed continued compliance during the DBT Phase may choose to enter a 12 week OLE Phase with daily dosing of rimegepant (75 mg QD) ODT. Open label study drug will be dispensed at the Day 35 visit for subjects who enter the OLE Phase. Subjects should take the first dose of OLE study drug on Day 36.

Subjects report study drug exposure in the subject paper study log (diary), whereas sites report study drug accountability on the Study Drug Dispensing Log CRF.

An administrative listing of IP batch numbers is provided for the treated analysis set. Refer to the Core SAP for listing contents.

DB Study Drug (Rimegepant or Placebo) Exposure

DB rimegepant or placebo exposure will be summarized descriptively by as-treated treatment groups for period 1 placebo, period 1 rimegepant, period 2 rimegepant, period 2 placebo, rimegepant pooled, placebo pooled and overall, and will include the following parameters:

- Time on DBT (days), derived as DBT end date – DBT start date + 1
- Time on DBT study drug category (weeks)
- Cumulative DBT exposure (mg), derived by summing number of DB mg across DB study drug records
- Average DBT exposure (mg per day), derived as cumulative DB exposure/time on DBT
- Total DBT exposure (tablets) summed across all subjects, derived by summing cumulative DB exposure across all subjects.
- Total DBT exposure (patient-years), derived by summing (DBT end date – DBT start date + 1)/365.25 across all subjects.

OL Rimegepant Exposure

OL rimegepant exposure will be summarized descriptively by treatment sequence and overall, and will include the following parameters:

- Time on OL rimegepant (days), derived as OL rimegepant end date – OL rimegepant start date + 1
- Time on OL rimegepant category (weeks)
- Cumulative OL rimegepant exposure (mg), derived by summing number of OL mg across records with non-missing OL rimegepant date/times.
- Average OL rimegepant exposure (mg per day), derived as cumulative OL rimegepant exposure/time on OL rimegepant
- Total OL rimegepant exposure (tablets) summed across all subjects, derived by summing cumulative OL rimegepant exposure across all subjects
- Total OL rimegepant exposure (patient-years), derived by summing (OL rimegepant end date – OL rimegepant start date + 1)/365.25 across all subjects.

DB or OL Rimegepant Exposure

DB or OL rimegepant exposure will be summarized descriptively by as-treated DB rimegepant pooled/OL rimegepant, DB placebo pooled/OL rimegepant and overall, and will include the following parameters:

- Time on DB or OL rimegepant (days), derived as DB or OL rimegepant end date – DB or OL rimegepant start date + 1
- Time on DB or OL study drug category (weeks)
- Cumulative DB or OL rimegepant exposure (mg), derived by summing number of DB or OL mg across records with non-missing DB or OL rimegepant date/times.
- Average DB or OL rimegepant exposure (mg per day), derived as cumulative DB or OL rimegepant exposure/time on DB or OL rimegepant.

- Total DB or OL rimegepant exposure (tablets) summed across all subjects, derived by summing cumulative DB or OL rimegepant exposure across all subjects. Total DB or OL rimegepant exposure includes missed dose days within a study phase and excludes the dosing break between study phases (i.e., (last dose day of DB study drug – first dose date of DB study drug + 1) – (number of days with a dosing break between the DB and OL phases)).
- Total DB or OL rimegepant exposure (patient-years), derived by summing (DB or OL rimegepant end date – DB or OL rimegepant start date + 1)/365.25 across all subjects.

A by-subject listing of study drug exposure will be provided for the treated analysis set.

6.2.6.2 *Drug Accountability and Compliance*

DB study drug accountability and compliance will be tabulated by as-treated treatment groups for period 1 placebo, period 1 rimegepant, period 2 rimegepant, period 2 placebo, rimegepant pooled, placebo pooled, and overall with the number and percentage of subjects in the following categories for the DB phase:

- Any bottle dispensed (Yes, No, Not Reported)
- DB study drug taken but not randomized
- Tablet count compliance < 80% from study drug start to study drug end in DB phase
- More than the required number of tablets administered on 1 day
- Did not return ≥ 1 bottle dispensed and discontinued study drug, defined as any of the following:
 - Randomized subjects who were not treated and did not return DB bottle dispensed
 - Treated subjects who did not return ≥ 1 DB bottle dispensed and discontinued DBT (i.e., non-missing DBT last date)
- Did not return any bottle dispensed and discontinued study drug
- No study drug taken for ≥ 3 days (not necessarily consecutive) in any 1 week
- Incorrect study drug taken (all the time; at least once)

OL study drug accountability and compliance will be tabulated overall for the OLE phase:

- Tablet count compliance < 80% from study drug start to study drug end in OLE phase
- More than the required number of tablets administered on 1 day
- Did not return ≥ 1 bottle dispensed and discontinued study drug, defined as: OL rimegepant treated subjects who did not return ≥ 1 OL rimegepant bottle dispensed and discontinued OL rimegepant (i.e., non-missing OL rimegepant last date).
- Did not return any bottle dispensed and discontinued study drug
- No study drug taken for ≥ 3 days (not necessarily consecutive) in any 1 week

A by-subject listing of treatment compliance will be provided for the treated analysis set.

6.2.6.3 *Non-study Medications*

Non-study medications will be identified from the Concomitant Medications and Rescue Pain Medications CRFs. Rescue medications are defined as non-study medications reported on the Rescue Pain Medication CRF. Rescue medication dates and times are not imputed.

Non-study medications will be summarized by therapeutic class and preferred name. For each subject, multiple records of the same medication will be counted only once within each therapeutic class and preferred name. Medications will be displayed in descending order of overall frequency within therapeutic class and preferred name, unless specified otherwise.

A by-subject listing of concomitant medications, inclusive of rescue medications, is provided by therapeutic class and preferred name for the enrolled subjects. Medication types are identified. Refer to the Core SAP for listing contents.

Refer to the Core SAP for non-study medication start and stop date imputation, listing content, and definition of concomitant medication.

DBT Period Non-study Medications

Frequency tables of the following DBT period non-study medications are provided by period 1 placebo, period 1 rimegepant, period 2 rimegepant, period 2 placebo, rimegepant pooled, and placebo pooled for the DBT treated subjects: concomitant medications, rescue medications. Medications are displayed in descending order of rimegepant pooled frequency within therapeutic class and preferred name.

OL Rimegepant Period Non-study Medications

OL rimegepant period non-study medications will be summarized analogously by treatment sequence and overall for the OL rimegepant treated subjects and the following medications: concomitant medications, rescue medications.

